10.3.3 Methods

Whole blood samples are being collected at baseline for DNA isolation and evaluation of genetic polymorphisms that affect antioxidant metabolism such as MnSOD. In addition, there is evidence of other interactions between antioxidant systems and dietary practice. Some of these could have an impact on the prostate such as catechol-o-methyl transferase and glutathione peroxidase.

10.4 Analysis of diagnostic prostate biopsy sections (Substudy 151105)

10.4.1 Background

A great deal of information is contained in the prostate tissue in the diagnostic biopsy: the Gleason score, which indicates the aggressiveness of the cancer, and the size and location of the cancer. Higher Gleason score and larger tumor are associated with disease progression. The biopsy tissue can be used to describe the rates at which prostate cells are proliferating and at which prostate cells are undergoing apoptosis. Together, these factors provide an indicator of overall tumor growth index, which is associated with disease progression. The biopsy also can be used to describe the degree to which androgen-signaling proteins, including the androgen receptor, and androgen metabolism enzymes, including 5-alpha reductase 1, 2, and 3, are expressed. Androgen-signaling proteins have been linked to prostate cancer risk and to treatment outcome, with androgen signaling generally associated with the presence or development of more aggressive disease (108-110). Recent advances make possible the detection of small noncoding segments of RNA, known as microRNA, which can be extracted from serum and from tissue fragments. MicroRNAs 141 and 375, which have received a great deal of attention as likely predictors of prostate cancer treatment outcome, will be examined in this study (111, 112). These two microRNAs have been associated with more aggressive disease and with tumor progression.

Taking these key indicators into account in analyses may enable better description of the likelihood that the prostate will respond to dietary change. Although randomized assignment should greatly lessen the likelihood of confounding of outcome by such

baseline characteristics as tumor growth, proteins predictive of outcome, or microRNA; taking these characteristics into account may increase the power of these analyses. In addition, it is possible that these factors may interact with treatment assignment to affect cancer progression.

10.4.2 Objectives

- 10.4.2.1** To compare proliferation, apoptosis and the tumor growth index to dietary intervention assignment as predictors of cancer progression in AS patients.
- 10.4.2.2** To compare proliferation, apoptosis and tumor growth index to outcome predictors among AS patients randomized to dietary intervention as opposed to those assigned to the comparison group.
- 10.4.2.3** To compare protein levels of the androgen receptor and 5-alpha reductase 1, 2, and 3 to dietary intervention assignment as predictors of cancer progression in AS patients.
- 10.4.2.4** To compare protein levels of the androgen receptor and 5-alpha reductase 1, 2, and 3 as outcome predictors among AS patients randomized to dietary intervention as opposed to those assigned to the comparison group.
- 10.4.2.5** To compare expression of microRNAs 141 and 375 to dietary intervention assignment as predictors of cancer progression in AS patients.
- 10.4.2.6** To compare expression of microRNAs 141 and 375 as outcome predictors among AS patients randomized to dietary intervention as opposed to those assigned to the comparison group.

10.4.3 Methods

Institutions will be asked to provide 10 x 5 um unstained sections that show cancer on charged glass slides from the formalin-fixed, paraffin-embedded, diagnostic prostate biopsy blocks to the Alliance Biorepository at The Ohio State University (see Section 6.2). Only one core should be placed on each slide. Label the slides with CALGB 70807 patient ID number, accession number, and order of sections.

The immunohistochemistry will be performed at Roswell Park Cancer Institute, under the direction of [REDACTED]. Commercially available antibodies will be used to immunostain the slides for the following: Ki-67 (proliferation), cleaved caspase 3 (apoptosis), androgen receptor, and 5-alpha reductases 1, 2, and 3. A panel of microRNAs will be extracted from the serum collected as part of sub-study CALGB 151105 (see Section 6.2.3). microRNA 141 and 375 expression will be assayed by procedures developed by Exiqon Laboratories (Blondal et al, 2013).

10.4.4 Statistical considerations

The baseline biomarkers will be associated with progression-free survival (PFS), time to progression as defined for the main study or death. Specific statistical analysis plans are as follows for each study objective. About 80% of the patients in the main study will participate in this correlative study. With $n = 334 (=418 \times 0.8)$ patients, a Cox regression model to regress PFS on a continuous biomarker will have 95% of power to detect a log-hazard ratio (or, regression coefficient of the Cox proportional hazards model) of 0.4 between two patient groups whose biomarker values are 1 standard deviation away with a two-sided alpha level of 5%. This power calculation is based on 85% of 2-year PFS for the whole population, the accrual and follow-up periods assumed for the main study and the assumption that each marker is normally distributed (possibly after a transformation).

- 10.4.4.1 To compare proliferation, apoptosis and the tumor growth index to dietary intervention assignment as predictors of cancer progression in AS patients**

PFS will be regressed on each biomarker of proliferation (KI-67), apoptosis (cleaved caspase 3) and tumor growth rate (a composite of proliferation and apoptosis) using a Cox regression model. In order to see which biomarkers are independently prognostic, we will also perform a Cox regression to regress PFS on all three of the biomarkers. We will repeat these regression analyses adjusting for treatment allocation to investigate if the effect of these biomarkers is confounded with treatment allocation.

10.4.4.2 To compare proliferation, apoptosis and tumor growth index to outcome predictors among AS patients randomized to dietary intervention as opposed to those assigned to the comparison group

The analyses adjusting for treatment allocation as described in in Section 10.4.4.1 will be repeated by adding the interaction term between each marker and treatment allocation to the regression models to see if the effect of each biomarker is different between the two treatment arms. If any of these interaction terms are significant, then we will also fit a regression model within each arm to develop a prediction model based on the biomarkers for each treatment arm.

10.4.4.3 To compare protein levels of the androgen receptor and 5-alpha reductase 1, 2, and 3 to dietary intervention assignment as predictors of cancer progression in AS patients

PFS will be regressed on each biomarker of androgen receptor, 5 alpha reductase 1, 5 alpha reductase 2, and 5 alpha reductase 3 using a Cox regression model. In order to see which of these protein level biomarkers are independently prognostic, we will also perform a Cox regression to regress PFS on all four of these biomarkers. We will repeat these regression analyses adjusting for treatment allocation to investigate if the effect of the biomarkers is confounded with treatment allocation.

10.4.4.4 To compare protein levels of the androgen receptor and 5-alpha reductase 1, 2, and 3 as outcome predictors among AS patients randomized to dietary intervention as opposed to those assigned to the comparison group

The analyses adjusting for treatment allocation as described in in Section 10.4.4.3 will be repeated by adding the interaction term between each marker and treatment allocation to the regression models to see if the effect of each biomarker is different between the two treatment arms. If any interaction terms are significant, then we will fit a regression model within each arm to develop a prediction model based on the biomarkers for each treatment arm.

10.4.4.5 To compare expression of microRNAs 141 and 375 to dietary intervention assignment as predictors of cancer progression in AS patients

PFS will be regressed on each biomarker of microRNAs 141 and 375 using a Cox regression model. In order to see which of these microRNAs are independently prognostic, we will also perform a Cox regression to regress PFS on both of the microRNAs. We will repeat these regression analyses adjusting for treatment allocation to investigate if the effect of these biomarkers is confounded with treatment allocation.

The microRNA package we are going to use will examine many more (~200) microRNA biomarkers. We will develop a prediction model for PFS using all the examined microRNA biomarkers as candidate predictors using the gradient lasso procedure,¹¹³ and compare the prediction power of this model with that based on microRNAs 141 and 375. A Cox regression will be conducted including the risk score fitted using the gradient lasso method and treatment allocation.

10.4.4.6 To compare expression of microRNAs 141 and 375 as outcome predictors among AS patients randomized to dietary intervention as opposed to those assigned to the comparison group

The analyses adjusting for treatment allocation as described in Section 10.4.4.5 will be repeated by adding the interaction term between each biomarker and treatment allocation to the regression models to see if the effect of each biomarker is different

between the two treatment arms. If any interaction terms are significant, then we will fit a regression model within each arm to develop a prediction model based on the biomarkers for each treatment arm.

In order to investigate the prediction power of the fitted model using the gradient lasso in Section 10.4.4.5, a Cox regression will be conducted including the risk score fitted using the gradient lasso method, treatment allocation and their interaction term.

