6.0 DATA SUBMISSION AND SAMPLE SUBMISSION

6.1 Data Submission

Forms should be submitted to the Alliance Statistics and Data Center (SDC) in compliance with the Data Submission Schedule below.

Forms must be submitted electronically using the “Submit to CALGB” button located at the bottom of the last page of each form. Any required forms, supporting documentation or amended forms that cannot be submitted electronically should be mailed directly to the Alliance Data Center for scanning and quality review at the address below:

Alliance Data Center

[Redacted address information]

For the most up-to-date forms, please visit the Alliance or CTSU web site.

Data Submission Schedule:

Form		Submission Schedule
	Pre-Registration Pre-Registration Worksheet	Submit at pre-registration
C-2010	MEAL Participant Contact Information Form	Submit to UCSD staff (See Sec. 5.2)
	Registration Registration Worksheet CALGB 70807 On Study Form	Submit within 2 weeks of registration
C-2002	CALGB 70807 Personal Habits Questionnaire	To be administered to patients at the pre-registration visit and submitted to the Alliance Statistics and Data Center within 2 weeks of registration.
C-2003	CALGB 70807 MAX-PC Form	
C-2004	CALGB 70807 Nutritional Self Efficacy Form	
C-2005	CALGB 70807 IPSS Form	
C-2023	CALGB 70807 EPIC-26 Form	
C-2007	CALGB 70807 FACT-P Form	
	During Intervention	
C-2013	CALGB 70807 Follow Up Form	Submit at 3, 6, 9, 12, 15, 18, 21, 24 months
C-2081	CALGB 70807 PSA Doubling Time Form	Submit at 6 months
C-2003	CALGB 70807 MAX-PC Form	Submit at 6, 12, 18 and 24 months
C-2005	CALGB 70807 I-PSS Form	
C-2023	CALGB 70807 EPIC-26 Form	
C-2007	CALGB 70807 FACT-P Form	
C-2004	CALGB 70807 Nutritional Self Efficacy Form	
C-2008	CALGB 70807 MEAL Study Counseling Evaluation Form	Arm A patients only: Submit at 12 and 24 months
	Post Intervention Follow-Up	
C-2013	CALGB 70807 Follow Up Form	Submit every 3 months until 2 years from date of registration (see Section 8.7)
	Other	
C-260	CALGB Remarks Addenda	Submit as needed

If a study participant chooses to withdraw from the study, submit the C-260 CALGB Remarks Addenda to the Alliance Data Center and copy by fax [REDACTED]

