11.0 STATISTICAL CONSIDERATIONS

11.1 Randomization

Patients will be randomized with equal probability to receive the dietary intervention (experimental arm) or dietary information (control arm). A total of 464 patients will be enrolled to this trial, 232 patients per arm. The study will take a total of 5 years: about 3 years of accrual with an expected accrual rate of 15 patients per month, and 2 years of follow-up for each patient.

Stratification factors: Randomization will be stratified by age (≤ 70 years vs. > 70 years), race (African American vs. Other) and baseline prostate biopsy (0-12 months prior to registration vs. >12 -24 months prior to registration).

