11.2 Design

Each patient will be followed for 24 months, and PSA will be evaluated every 3 months starting from baseline. Prostate biopsies are taken at baseline and 24 months.

The primary outcome of interest in this prevention trial is disease progression defined by (a) PSA doubling time (PSADT) < 3 years, (b) PSA ≥ 10 at any time, or (c) Gleason sum on repeat biopsy ≥ 7 for men younger than 70 years and $\geq 4+3 = 7$ for men 70 years or older. These criteria are drawn from one of the largest active surveillance studies to date, the Toronto cohort (12). Data from this cohort indicate that approximately 20% of patients on active surveillance will progress by these criteria: 14% by PSA doubling time and 8%-10% by Gleason score.

Thus, using the log-rank test with a two-sided $\alpha = 5\%$, a sample size of 418 will provide 80% power to detect a difference in progression rate (PGR) of 20% in the control and 10% in the experimental arm during 24 months of follow-up. Under the exponential distributions for the time to progression, the 2-year PGR of 20% vs. 10% corresponds to a hazard ratio (HR) of 2.118. Assuming 10% of dropout rate (including patients who are treated before progression), a total of 464 patients will be enrolled to this trial.

Centralized pathology review will be conducted on the tissue specimens of the first 50 patients. From an analysis of grading by community vs. Johns Hopkins pathologists, Gleason grading of adenocarcinoma in prostate needle biopsy tissue (106), Gleason score was changed from 3+4 by community review to 4+3 by Johns Hopkins review for about 14% of men and from 6 or below to 7 or above for about 8% of men. Assuming about 30% of men in this study will be >70 years old and these two types of changes occur uniformly over the whole range of age, we believe that no more than 10% of men will become ineligible for the study by the centralized pathology review. We will consider increasing the sample size by a maximum of 10% depending on the proportion of men who become ineligible by central pathology review.

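### The biomarker sub-study's stated 95% power is about 81% under the 24-month follow-up that the protocol gives every patient

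*Combined protocol and SAP*

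**What the plan says.** Section 10.4.4 contains the only power statement for the tissue and microRNA objectives of Section 10.4. It starts from participation: "About 80% of the patients in the main study will participate in this correlative study", which gives 418 × 0.8 = 334 patients. It then states that "a Cox regression model to regress PFS on a continuous biomarker will have 95% of power to detect a log-hazard ratio" "of 0.4 between two patient groups whose biomarker values are 1 standard deviation away with a two-sided alpha level of 5" per cent. The basis is given next: "This power calculation is based on 85% of 2-year PFS for the whole population, the accrual and follow-up periods assumed for the main study", together with a normally distributed marker.

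The main study's periods are set out elsewhere:

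- Section 11.1 plans about 3 years of accrual and "2 years of follow-up for each patient".
- Section 11.2 says "Each patient will be followed for 24 months".
- The schedule in Section 6.1 ends the follow-up form at the same point: "Submit every 3 months until 2 years from date of registration".
- Section 8.7.3 keeps follow-up to two years even for men who progress or start therapy.
- Section 11.4.1 places the final analysis 2 years after accrual closes, when the last patient reaches 24 months.

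**The concern.** When every patient is followed for the same 24 months, the length of accrual has no effect on the final number of events. It matters only if early entrants stay under observation until a common calendar cut-off. A power figure that cites the accrual period therefore suggests that the calculation assumed longer follow-up than the protocol provides.

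The figure describes how well a single marker's association with PFS can be detected, which is the analysis for objectives 10.4.2.1, 10.4.2.3 and 10.4.2.5. If it is too high, the chance of missing a real association of the planned size is understated. A reader who relies on the stated 95% could then take a null marker result as stronger evidence of no association than it is. Objectives 10.4.2.2, 10.4.2.4 and 10.4.2.6 add marker-by-arm interaction terms to the same models. They have no power statement of their own, and their power is lower still.

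**Working it through.** **Inputs from the documents**

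- n = 334, log-hazard ratio β = 0.4 per standard deviation, two-sided α = 0.05, 2-year PFS 85%, normal marker (Section 10.4.4)
- Accrual about 3 years; 24 months of follow-up per patient (Sections 11.1 and 11.2)
- No further deduction for dropout, because 334 is taken from the 418 and not from the 464 enrolled

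**Formula.** For a continuous covariate scaled to standard deviation 1, with D events:

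power = Φ(β√D − 1.96)

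Events needed for 95% power: (1.960 + 1.645)² / 0.4² = 81.2.

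**1. Reproducing the stated 95%.** Assume exponential PFS with hazard h = −ln(0.85)/2 = 0.0813 per year, uniform accrual over 3 years and a common cut-off at year 5, so that follow-up runs from 2 to 5 years.

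- P(event) = 1 − [exp(−2h) − exp(−5h)]/(3h) = 0.2457
- D = 334 × 0.2457 = 82.1
- Power = Φ(0.4 × √82.1 − 1.96) = 95.2%

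**2. The follow-up actually planned.** Every patient stops at 24 months.

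- D = 334 × 0.15 = 50.1
- Power = Φ(0.4 × 7.078 − 1.96) = Φ(0.871) = 80.8%

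**3. Simulation.** The Cox Wald test was simulated with a normal marker and marginal 2-year PFS of 85%, in two independent runs of 3,000 and 4,000 trials.

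| Follow-up | Formula | Simulation |
|---|---|---|
| 24 months for all | 80.8% | 80.4%, 80.1% |
| 2 to 5 years | 95.2% | 93.9%, 94.5% |

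**4. Other readings, all at 24 months**

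| Patients | Test at 5% | Power |
|---|---|---|
| 334 | one-sided | 88.2% |
| 371 (0.8 × 464) | two-sided | 84.7% |
| 418 | two-sided | 88.6% |
| 464 | two-sided | 91.6% |
| 418 | one-sided | 93.6% |
| 464 | one-sided | 95.5% |

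Only the last two come near 95%, and both contradict the stated sample size and the stated sidedness.

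**5. Cross-check against the main trial.** The hazard ratio is ln(0.8)/ln(0.9) = 2.118. Freedman's formula gives about 61 events, or 62 after rounding up to an even number. Dividing by the average 24-month event rate of 0.15 gives 407 to 413 patients, close to the stated 418. With 2 to 5 years of follow-up only about 230 (Schoenfeld) to 254 (Freedman) would be needed. The main sample size therefore fits a fixed 24 months, and the sub-study figure departs from the design it cites.

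**6. What 50 events support**

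- 95% power requires β = (1.960 + 1.645)/√50.1 = 0.51, a hazard ratio of 1.66 per standard deviation instead of 1.49.
- 95% power at β = 0.40 would need 81.2/0.15 ≈ 541 patients, more than the 464 the whole trial enrols.

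**7. Interactions, for illustration.** Assume a between-arm difference of 0.4 in the marker's log-hazard ratio, 167 sub-study patients per arm, and 24-month event rates of 20% and 10%. That gives 33.4 and 16.7 events. The standard error is √(1/33.4 + 1/16.7) = 0.30, and power is Φ(0.4/0.30 − 1.96), about 27%.

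**The case against.** The arithmetic is not in dispute. The case on the other side concerns weight, scope and cause.

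- **Weight.** The sub-study is optional, and 334 is simply 80% of the main trial's 418. No sample size, test or stopping rule depends on the 95%. The corrected 81% is about the 80% that the main trial accepts for its primary endpoint. All of this stands. It limits the consequences but does not make the stated figure right.
- **Scope.** The sentence covers the main effect of one marker, so it speaks to three of the six objectives. The interaction objectives claim no power. This also stands: their lower power is a related gap, not part of the misstated number.
- **Cause.** The documents do not say how 95% was obtained. Accrual is only about 3 years; at 15 patients per month, 418 to 464 patients take 28 to 31 months, which with 2 further years gives 93.5% to 94.2%. Simulation of the 3-year case gives about 94%. The staggered cut-off is therefore a likely explanation, not a proven one. The error does not depend on it, because the stated inputs give about 81% whatever the origin.
- **Over-reading a null result.** The planned analyses nowhere use planning power to interpret a null finding, and the hazard ratio and its uncertainty would be available. That risk is possible rather than built into the plan.
- **The replacement is conditional too.** It assumes that all 334 patients supply usable specimens and yield the full 15% of events, and that each marker is tested at an unadjusted 5%. These assumptions should be written beside the number.

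**Conclusion.** The concern holds. On the plan's own inputs and its 24-month follow-up, the power for a log-hazard ratio of 0.40 per standard deviation is 80.8% by formula (about 80% by simulation), not 95%. The overstatement is 14 percentage points, and the type II error is 19%, nearly four times the implied 5%. At the stated sample size and two-sided test, no 24-month reading reaches 95%.

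The result rests on 85% 2-year PFS, one standardised normal marker at an unadjusted two-sided 5%, and 334 evaluable patients. Counting 80% of all 464 enrolled would raise it only to 84.7%. Unusable specimens or a multiplicity adjustment across markers would lower it. The primary endpoint's sample size is not affected.

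**What to change.** Replace the power sentence in Section 10.4.4 with wording such as:

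> With 334 evaluable patients, each followed for 24 months, and 85% 2-year PFS (about 50 events), a Cox model for a single normally distributed marker has 81% power at a two-sided 5% level for a log-hazard ratio of 0.40 per standard deviation (hazard ratio 1.49), and 95% power for 0.51 (hazard ratio 1.66). No adjustment is made for the number of markers tested.

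Delete the reference to the accrual period, which has no bearing when follow-up is fixed per patient. Say that the figure applies to the single-marker analyses of objectives 10.4.2.1, 10.4.2.3 and 10.4.2.5, and that no power is claimed for the interaction objectives. If longer PFS follow-up was in fact intended for the sub-study, Sections 6.1, 8.7.3, 11.1 and 11.2 would have to provide for it, which they do not at present.

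The cost is a short text change and a less favourable stated power. Sample size, data collection and planned analyses stay as they are.

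### The joint Cox model for Ki-67, cleaved caspase 3 and the tumour growth index includes an index determined by the other two, so it cannot show which is independently prognostic

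*Combined protocol and SAP*

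**What the plan says.** Section 10.4.1 explains that biopsy tissue yields a proliferation rate and an apoptosis rate, and adds: "Together, these factors provide an indicator of overall tumor growth index". Section 10.4.3 lists the stains. Those that serve this objective are "Ki-67 (proliferation), cleaved caspase 3 (apoptosis"), and no separate assay is listed for the index.

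Section 10.4.4.1 regresses PFS on each of three markers: Ki-67, cleaved caspase 3 and "tumor growth rate (a composite of proliferation and apoptosis"). It then adds a joint model, with its purpose stated: "In order to see which biomarkers are independently prognostic", "we will also perform a Cox regression to regress PFS on all three of the biomarkers". These regressions are repeated with treatment allocation added. Section 10.4.4.2 repeats the treatment-adjusted analyses with marker-by-arm interaction terms. If an interaction is significant, a prediction model is to be developed within each arm.

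No formula or scale for the index appears in sections 10.4.1 to 10.4.4. Nor do they give a rule for collinearity or for dropping a term.

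**The concern.** Asking which of several markers is independently prognostic presumes that each can vary while the others are held fixed. That is impossible here: once Ki-67 and caspase 3 are known, so is the index. The model therefore has three covariates but only two measured quantities.

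Two things are at stake. First, a growth index that really tracks progression could be reported as not independent simply because its own components sit beside it in the model. Second, the analyst may have to choose after seeing the data which term to drop or which index formula to use. The redundancy carries into the treatment-adjusted joint model and the joint interaction model of 10.4.4.2. The panels in 10.4.4.3 (androgen receptor and three 5-alpha reductases) and 10.4.4.5 (microRNAs 141 and 375) do not have this problem, because their markers are measured separately.

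**Working it through.** **Inputs from section 10.4.4.** n = 334; 2-year PFS 85%; log-hazard ratio 0.4 per SD for one continuous marker; two-sided alpha 5%; stated power 95%. Section 11.1 gives about 3 years of accrual and 2 years of follow-up per patient. No power is stated for the three-marker model.

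**The plan's own figure.** Power for one marker is Φ(0.4·√D − 1.96), where D is the number of events.
- With 2 years per patient, D = 334 × 0.15 = 50.1. Then 0.4 × 7.08 − 1.96 = 0.87, so power is 80.8%.
- Power of 95% needs D = (1.96 + 1.645)² / 0.4² ≈ 81. Exponential PFS with follow-up running to study end (2 to 5 years) gives about 82 events and 95.2%.

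So the stated 95% is reached only with longer follow-up than section 11.1 allows. That is a separate matter. It is shown here because both event counts are used below.

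**Case 1: index linear in its components.** Let K and A be Ki-67 and caspase 3 on the modelled scale, with index I = K − A. This also covers a log-ratio when K and A are logged. The log-hazard is

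b1·K + b2·A + b3·(K − A) = (b1 + b3)·K + (b2 − b3)·A.

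Only the two sums are identified. For any constant c, the coefficients (b1 − c, b2 + c, b3 + c) fit equally well. The three columns have rank 2, and in simulation the design was singular in 500 of 500 trials, as the algebra requires. If all three arm interactions enter together, K×arm, A×arm and I×arm have the same dependency, so the six marker columns have rank 4.

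**Case 2: index non-linear, for example I = K/A.** The design has rank 3, and the model fitted in 500 of 500 simulated trials. The coefficients do not answer the question, however.
- Holding A and K/A fixed also fixes K, so the coefficient of K has no contrast with the others held constant. The same is true of A.
- Holding K and A fixed also fixes K/A. The index coefficient therefore measures only curvature beyond the two component terms.

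**Loss of precision in case 2.** The documents give no marker distribution. Assume lognormal markers with CV 0.3 to 1.0, log-scale correlation 0 to 0.6, and various pairings of raw and logged terms. The variance inflation factor (VIF) of the index then runs from about 1.7 to 29. Power for the index becomes Φ(0.4·√(D/VIF) − 1.96): about 58% down to 8% at 50 events, and about 79% down to 10% at 82 events.

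**Illustration.** Trials of 334 patients were simulated with 24 months of follow-up (about 53 events), CV 0.6 and correlation 0. The hazard was driven by the log-ratio of the markers at 0.4 per SD, and the fitted index was the raw ratio.

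| Components in the model | Index significant, alone | Index significant, joint | No marker significant, joint |
|---|---|---|---|
| Raw | 75.6% | 11.8% | 64.0% |
| Logged | 74.2% | 5.2% | 55.4% |

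In the second row the logged components already carry the whole true effect, so 5.2% is about the false-positive rate. The index looks prognostic alone and empty in the joint model, although the balance of the two markers is what drives the hazard.

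**The case against.** The strongest reply is that several stronger readings go beyond the text. Each of these is something a reader might infer, and the documents do not support it.

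- *The joint model cannot be fitted.* This is true only in case 1. No formula is given, and a raw-ratio index fits without difficulty.
- *The plan commits to logged markers, so a ratio index must be singular.* The words "the assumption that each marker is normally distributed (possibly after a transformation") state an assumption of the single-marker power calculation. They do not say how the markers enter the joint model.
- *Objectives 10.4.2.1 and 10.4.2.2 cannot be met.* Each marker is first modelled alone, with and without treatment. Those models, and interactions added to them, remain valid and address the objectives.
- *The within-arm prediction models inherit the fault.* Section 10.4.4.2 does not say they contain all three terms. Even under exact collinearity, dropping one redundant term leaves the fitted risk score unchanged.

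It can also be said that a non-linear index term is a legitimate one-degree-of-freedom test of whether the ratio adds to its components. It is, but that question is narrower than the one the section poses. Finally, the precision figures rest wholly on assumed distributions, and this is one regression in an optional correlative substudy. Both points are right, and they limit the weight of the finding. They do not rescue the joint model for its stated purpose.

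**Conclusion.** The point holds for the joint model. It follows from the plan's own description of the index as a composite of the other two covariates, and it needs no numerical assumption. The coefficients are not estimable if the index is linear in its components on the modelled scale. Otherwise they are estimable but do not measure independent prognostic value. The treatment-adjusted joint model and the joint interaction model share the fault.

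No firm size can be given, because the index formula and the marker distributions are not in the documents. The VIF range of about 1.7 to 29 and the fall from about 75% to 5–12% are illustrations under the stated assumptions.

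The change should be made because the rule as written does not do what it says. It does not affect the trial's primary analysis or the single-marker results.

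**What to change.** In 10.4.4.1 and 10.4.4.2, replace the three-marker model with:

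1. a joint Cox model of Ki-67 and cleaved caspase 3 only;
2. a separate Cox model of the growth index alone, with its formula and scale fixed before the data are examined.

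Compare the two by AIC. Use a likelihood-ratio test of the coefficient constraint (equal and opposite coefficients) only if the index is a difference or log-ratio on the same scale as its components. For a raw ratio the two models are not nested and that test does not apply. Repeat each model with treatment added, and add arm interactions to each model separately.

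The cost is a few sentences of text, with no extra samples, assays or patients.
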